2 STUDY OBJECTIVES

2.1 Primary Objective

To evaluate the disease progression using a Amyotrophic Lateral Sclerosis Functional Rating Scale – Revised (ALSFRS-R) and the forced vital capacity (FVC) of subjects affected by ALS treated with plasma exchange (PE) with Albutein 5%.

2.2 Secondary Objectives

To evaluate the effects of PE using Albutein 5% on:

- Cognitive dysfunction
- Beta-methylamino-L-alanine (BMAA) chronic toxicity
- Neurofilament levels
- Systemic inflammatory response

2.3 Safety Objectives

- Safety and tolerability of the procedure, including adverse events (AEs), clinical laboratory testing, physical examination, and vital signs.

3 OVERALL STUDY DESIGN

3.1 Overview of study design

This is a pilot, phase IIa, prospective, open-label and single-arm study, for a period of 12 months (six months of PE treatment with Albutein 5% and six months of follow-up after last PE).

[figure not shown]
The six-month (24 weeks) treatment period consists in an Intensive Treatment Phase of 2 PEs per week over 3 weeks (6 PEs in total), followed by a Maintenance Treatment Phase of one

weekly PE for 21 weeks (21 PEs). In total, 27 PEs will be conducted during the overall treatment phase.

The following six visits are scheduled:

- Baseline Visit (V0), that will extend through a maximum of 3 weeks. Week 0 is defined as the week immediately prior to when the first PE is performed allowing to all other visits to be subsequently scheduled.
- Evaluation Visit (V1), will take place during week 4 once the Intensive Treatment Phase is completed, on the same day but before the PE#7 procedure.
- Evaluation Visit (V2), will take place at week 12 in the middle of the Maintenance Treatment Phase, before the PE#15 procedure in 2 consecutive days.
- Evaluation Visit (V3), will take place during week 24 for the purpose of finalizing the treatment period, on the same day but before the last scheduled PE#27 procedure.
- Follow-up Visit (V4), will take place 7 days after the last PE#27, on week 25, where the subject will come to the DHMC facilities.
- Follow-up Visit (V5), will be scheduled on week 36 (± 7 days) corresponding to the middle point of the follow-up phase.
- Final Study Visit (V6), will take place during week 48 (± 7 days) corresponding to the end of study.

The design can be visualized with the following chart:

More details are available in the Study Protocol concerning the examinations, tests, etc. that will be performed during each visit.

3.2 Study population

Subjects, males or females, who are older than 18 years of age and younger than 70, who have an ALS diagnosis, and who give their consent to participate after having been duly provided signed informed consent by the investigator may be included in this study.

Both untreated subjects and subjects on a stable dose of Riluzole for at least 28 days may be enrolled.

3.2.1 Inclusion criteria

1. Signed informed consent.

2. Subjects over 18 years of age and less than 70 years old.
3. Subjects with a possible, probable-lab supported, probable, or definite diagnosis of ALS, according to the revised El Escorial criteria.
4. Subjects having experienced their first ALS symptoms within 18 months prior to recruitment/consent.
5. FVC >70%.
6. Subjects must be medically suitable for study participation and willing to comply with all planned aspects of the protocol, including blood sampling, at the time of inclusion in the study.

3.2.2 Exclusion criteria

1. Subjects with pre-existing clinically significant lung disease not attributable to ALS.
2. Subjects diagnosed with other neurodegenerative diseases associated with other motor neuron dysfunction.
3. Participation in another investigational product study within one month prior to screening.
4. Females who are pregnant, breastfeeding, or, if of child-bearing potential, unwilling to practice a highly effective method of contraception (oral, injectable or implanted hormonal methods of contraception, placement of an intrauterine system, condom or occlusive cap with spermicidal foam/ gel/ film/ cream/ suppository, male sterilization, or true abstinence) throughout the study.
5. Difficult or problematic peripheral vein access and inability to implant a central catheter which would make continuous PE not feasible as per the visit protocol.
6. Contraindication to undergo PE or subject has abnormal coagulation parameters at the discretion of Outpatient Apheresis Unit team, including but not limited to:
 - a) Thrombocytopenia (platelets <100,000/ μ L)
 - b) Fibrinogen <1.5 g/L
 - c) International Normalized Ratio (INR) >1.5
 - d) Beta-blocker treatment and bradycardia <50 beats/min
 - e) Treatment with angiotensin-converting enzyme inhibitors which may increase the risk of allergic reactions
7. History of anaphylaxis or severe systemic response to any plasma-derived albumin preparation, component of Albutein 5%, or other blood product(s).
8. Subjects unable to interrupt treatment with acetylsalicylic acid, other oral antiplatelet, or anticoagulant.

9. Renal dysfunction by elevated creatinine concentration >2 mg/dL.
10. Presence of heart disease that contraindicates PE treatment, including ischemic cardiopathy and congestive heart failure.
11. Presence of prior behavioral disorders requiring pharmacological intervention with less than 3 months of stable treatment.
12. Mentally challenged subject who cannot give independent informed consent.
13. Any condition that would complicate compliance with the study protocol (i.e., illness with the expectation of less than one year survival, abuse of drugs or alcohol, etc.).

3.3 Determination of sample size

There has been no formal calculation for the sample size since this is a pilot study. The number of subjects planned to be included in this study is 10 subjects completing the planned treatment. The sample size is considered adequate for the evaluation of the objectives of the study. In addition, there is a rising consensus in the ALS field that active control group comparisons should be avoided in early trials (19).

Lastly, the current EMA guidance document, *Guideline on clinical investigation of medicinal products for the treatment of amyotrophic lateral sclerosis (ALS) (EMA/CHMP/4015/2013)* states that the average functional decline is about 1 point per month in untreated subjects on the ALSFRS-R Functional Scale (20). Thus, it may be assumed that 10 subjects followed during 1 year of the clinical trial would be sufficient to evaluate a change of disease progression rate. In the event that a move towards stabilization is observed, the subsequent confirmatory studies will require a formal calculation for the sample size.

4 EFFICACY AND SAFETY VARIABLES

4.1 Primary efficacy variable

- Changes from baseline in the ALSFRS-R Functional Scale (5 post-baseline measurements: Weeks 4, 12, 25, 36, and 48),
- Changes from baseline in the FVC (5 post-baseline measurements: Weeks 4, 12, 25, 36, and 48).

4.2 Secondary efficacy variables

- Changes from baseline in cognitive function determined by the Amyotrophic Lateral Sclerosis – Cognitive Behavioral Screen (ALS-CBS) test (2 post-baseline measurements: Weeks 25 and 48),
- Changes from baseline in the motor evoked potential in thenar and hypotenar eminence and anterior tibialis muscle determined by electromyography (EMG) (5 post-baseline measurements: Weeks 4, 12, 25, 36, and 48),
- Evaluation of quality of life using the Amyotrophic Lateral Sclerosis Assessment Questionnaire 40 (ALSA-Q40) test (2 post-baseline measurements: Weeks 25 and 48),

- Changes from baseline in plasma cytokine panel and neurofilament analysis (8 post-baseline measurements: Weeks 4*, 12*, 24*, 36, and 48),
- Changes from baseline in Cerebrospinal Fluid (CSF) cytokine panel and neurofilament analysis (2 post-baseline measurements: Weeks 12 and 25)
- Changes from baseline in plasma BMAA levels (8 post-baseline measurements: Weeks 4*, 12*, 24*, 36, and 48),
- Changes from baseline in CSF BMAA levels (2 post-baseline measurements: Weeks 12 and 25),
- Changes from baseline in plasma immune population profile (3 post-baseline measurements: Weeks 4, 12, and 48).

* In those selected visits, there will be 2 measurements of biomarkers: before and after the PE procedure.

4.3 Safety variables

The following safety variables will be assessed:

- Percentage of PE sessions associated with at least one adverse reaction (AR) during or within 72 hours after the completion of the product infusion,
- Percentage of PE sessions temporarily associated with at least one AE, irrespective of causality, during or within 72 hours after the completion of the product infusion,
- Incidence of all AEs,
- Vital signs recorded at each assessment visit, before, during, and after each PE session, and as deemed necessary by the investigator,
- Pulse oximetry measurements recorded before, during, and after each PE session,
- Clinical laboratory testing (coagulation, blood count, biochemistry, and/or serology) at the specified visit.

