7.1.3.2. Suspected Adverse Reactions/Adverse Reactions

All noxious and unintended responses to a medicinal product or study treatment related to any dose should be considered suspected ARs. The phrase “responses to a medicinal product” means that a causal relationship between a medicinal product or study treatment and an AE is at least a reasonable possibility, that is, the relationship cannot be ruled out. In the framework of this study, a suspected AR with a causal relationship of “definite” will be labeled as an AR; thus, ARs are a subset of suspected ARs. The Sponsor is responsible for assessing the suspected AR expectedness during the clinical trial.

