7.1.3.3. Causality of Adverse Event

The Investigator is required to provide a causality assessment for each AE reported to the Sponsor. The Sponsor will consider the Investigator’s causality assessment. Assessment of the causal relationship to the study drug will be made according to the following classifications based on Karch FE, et al.(67)

- **Definite:** an event that follows a reasonable temporal sequence from administration of the treatment or in which the treatment level has been established in body fluids or tissues; that follows a known response pattern to the suspected treatment; and that is confirmed by improvement on stopping the treatment (dechallenge), and reappearance of the event on repeated exposure (rechallenge).
- **Probable:** an event that follows a reasonable temporal sequence from administration of the treatment; that follows a known response pattern to the suspected treatment; that is confirmed by dechallenge; and that could not be reasonably explained by the known characteristics of the subject's clinical state.
- **Possible:** an event that follows a reasonable temporal sequence from administration of the treatment that follows a known response pattern to the suspected treatment but that could have been produced by the subject's clinical state or other modes of therapy administered to the patient.
- **Doubtful/Unlikely:** an event that follows a reasonable temporal sequence from administration of the treatment; that does not follow a known response pattern to the suspected treatment; but that could not be reasonably explained by the known characteristics of the subject's clinical state.
- **Unrelated:** any event that does not meet the criteria above.

The operational tool to decide the AE causal relationship is based on algorithms by Karch et al. and Naranjo et al.(68,69) When an AE is classified, assessing causal relationship by the Investigator, as "definite", "probable," "possible" or "doubtful/unlikely," the event will be defined as a suspected AR. A suspected AR with a causal relationship of "definite" will be defined as an AR. When the causal relationship is labeled "unrelated," then it will be considered that the AE is not imputable to the study treatment and it is not a suspected AR.

In addition, when a causal relationship between the study treatment and the AE cannot be ruled out by the Investigator and/or Sponsor, it means that the AE cannot be labeled "unrelated."

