6.3.8 Adverse events

The Safety Analysis will be based on the safety population.

For summary purposes, adverse events (AEs) will be classified as treatment emergent AEs (TEAEs) or non-treatment emergent AEs (non-TEAEs) depending on the comparison of AE onset date/time with the start of study treatment treatment (i.e., start of PE#1). A TEAE will be defined as an AE which occurred on or after the start of study treatment. Non-TEAEs and TEAEs will be summarized separately.

The number of subjects with any TEAE and the total number of TEAEs will be presented in a summary table, and the characteristics of these adverse events will be described: number of subjects with, and total number of: serious TEAEs, TEAEs leading to death, severe TEAEs, TEAEs related to study drug, TEAEs related to study procedure, TEAEs leading to discontinuation from the study.

In a similar table, the number of subjects with, and the total number of: non-TEAEs, serious non-TEAEs, severe non-TEAEs will be presented.

The proportion of PE sessions temporarily associated with at least one AR (defined as occurring during or within 72 hours after the completion of the product infusion) will be summarized.

The proportion of PE sessions temporarily associated with at least one TEAE, irrespective of causality, during or within 72 hours after the completion of the product infusion, will also be summarized.

The number of subjects with any TEAE will be tabulated and summarized. AEs will be coded in accordance with the Medical Dictionary for Regulatory Activities (MedDRA) AE classification (version 17.0 or higher), and will be tabulated by system organ class (SOC) and preferred term (PT), presented in alphabetic order. This will be done overall, and by severity, causality, and seriousness levels.

Severity (or intensity) of AE:

AEs are classified according to their severity gradation as Mild, Moderate, and Severe.

Causality (relationship) of AE:

AEs will be considered related to the study drug when causality is “definitive”, “probable”, “possible” or “doubtful/unlikely” and such an event will be defined as a suspected AR. A suspected AR with a causal relationship of “definite” will be defined as an AR. On the other hand, when causality is “unrelated”, AEs will be considered as not related to the study drug.

Same rules will apply to define AEs related to study procedure.

In the table presented by causality, 4 classes of causality will be defined:

- related to study drug only

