- related to study procedure only
- related to both study drug and study procedure
- not related

Seriousness of AE:

AEs will be distinguished between serious and non-serious AEs, according to the view of either the investigator or Sponsor, depending on its outcome.

Each subject is counted once within each unique SOC and PT level. For example, if a subject has two headaches, the subject is counted only once under the PT “Headache” (worst case in terms of severity, causality, and seriousness will be chosen). Likewise, each subject is counted only once at each SOC level although they may have several different PT events within the same SOC.

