- Table 14.3.1.2 Summary of TEAEs – Safety Population
- Table 14.3.1.3 PE sessions temporarily associated with AR, occurring during or within 72 hours after the completion of the product infusion – Safety Population
- Table 14.3.1.4 PE sessions associated with TEAE, occurring during or within 72 hours after the completion of the product infusion – Safety Population
- Table 14.3.1.5 TEAEs: MedDRA coding by SOC and PT – Safety Population
- Table 14.3.1.6 TEAEs: MedDRA coding by severity, SOC and PT – Safety Population
- Table 14.3.1.7 TEAEs: MedDRA coding by causality, SOC and PT – Safety Population
- Table 14.3.1.8 TEAEs: MedDRA coding by seriousness, SOC and PT – Safety Population

List of deaths and other serious adverse events

- Table 14.3.2.1 Adverse events leading to death – Enrolled Population
- Table 14.3.2.2 Adverse events leading to discontinuation from the study – Enrolled Population
- Table 14.3.2.3 Serious adverse events – Enrolled Population

Laboratory data

- Table 14.3.3.1 Complete Blood Count: absolute values and change from baseline by visit – Safety Population
- Table 14.3.3.2 Complete Blood Count: summary of shift of values by visit – Safety Population
- Table 14.3.3.3 Biochemistry and Lipid Profile: absolute values and change from baseline by visit – Safety Population
- Table 14.3.3.4 Biochemistry and Lipid Profile: summary of shift of values by visit – Safety Population
- Table 14.3.3.5 Serum Electrolytes: absolute values and change from baseline by visit – Safety Population
- Table 14.3.3.6 Serum Electrolytes: summary of shift of values by visit – Safety Population
- Table 14.3.3.7 Coagulation: absolute values and change from baseline by visit – Safety Population
- Table 14.3.3.8 Coagulation: summary of shift of values by visit – Safety Population
- Table 14.3.3.9 Fibrinogen: absolute values and change from baseline by visit – Safety Population
- Table 14.3.3.10 Fibrinogen: summary of shift of values by visit – Safety Population
- Table 14.3.3.11 Serology results by visit – Safety Population

Concomitant therapy

Table 14.3.4.1 Prior medication – Safety Population
Table 14.3.4.2 Concomitant medication – Safety Population

Other safety data

Table 14.3.5.1 Vital signs during evaluation visits: absolute and change from baseline values by visit – Safety Population
Table 14.3.5.2 Vital signs during PE: change from pre-PE assessments – Safety Population

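### The percentage of PE sessions with an AR counts only events graded 'definite', so a related reaction that never recurs, or that ends PE before any re-exposure, scores zero; no session-level suspected-AR percentage is planned

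*SAP*

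**What the plan says.** The session variable appears in Protocol 6.1.3 and, in the same words, in SAP 4.3: "Percentage of PE sessions associated with at least one adverse reaction (AR) during or within 72 hours after the completion of the product infusion". SAP 6.3.8 plans its summary, and SAP Appendix 1 assigns it Table 14.3.1.3, titled "PE sessions temporarily associated with AR, occurring during or within 72 hours after the completion of the product infusion".

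The meaning of AR is fixed in both documents. SAP 6.3.8: "A suspected AR with a causal relationship of “definite” will be defined as an AR". Protocol 7.1.3.2 gives the same definition and concludes that "ARs are a subset of suspected ARs". Events graded probable, possible or doubtful/unlikely are suspected ARs but not ARs.

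Protocol 7.1.3.3 describes a 'definite' event as one that, among other conditions, is "confirmed by improvement on stopping the treatment (dechallenge), and reappearance of the event on repeated exposure (rechallenge"). The next grade down, 'probable', needs dechallenge but not rechallenge. The same section adds: "The operational tool to decide the AE causal relationship is based on algorithms". It cites these algorithms but does not reproduce them.

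The second session-level output is Table 14.3.1.4, sessions with any TEAE irrespective of causality. Related TEAEs, meaning definite through doubtful/unlikely, are summarized in SAP 6.3.8 by number of subjects and number of events. Table 14.3.1.7 tabulates TEAEs by causality in four classes: drug only, procedure only, both, not related.

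**The concern.** In everyday use, the percentage of sessions with an adverse reaction is read as the share of sessions with a treatment-related event. Here it is the strictest tier of causality. A clear one-off reaction, or one that makes a subject stop at its first appearance, is left out of it if the written definition is applied.

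Other parts of the plan use the broad tier. The related-TEAE summaries in SAP 6.3.8 and the stopping rules in Protocol 4.4 both run from definite to doubtful/unlikely. The report could therefore show several subjects with drug-related TEAEs beside an AR percentage of 0% of sessions, with nothing in the table to explain the difference. What is at stake is the statement the trial can make about tolerability per session, in a study whose safety objective is the safety and tolerability of the procedure.

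**Working it through.** **Step 1. Which events can enter the numerator.** Applying Protocol 7.1.3.3 as written, and assuming the other conditions for each grade are met:

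| Course of a related reaction | Rechallenge positive? | Can it be an AR? | Suspected AR? |
|---|---|---|---|
| Occurs once, later sessions uneventful | No | No | Yes |
| First occurrence ends PE | Not tested | No | Yes |
| Recurs at a later session | Yes | Yes | Yes |
| Recurs, then ends PE | Yes | Yes | Yes |

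**Step 2. What the planned tables pin down.** ARs are a subset of suspected ARs, and every suspected AR in the window is a TEAE. With the same sessions, window and causality basis:

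AR% (Table 14.3.1.3) ≤ suspected-AR% (not planned) ≤ all-TEAE% (Table 14.3.1.4).

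**Step 3. Denominator.** Protocol 5.1 and SAP 3.1 give 2 PEs x 3 weeks + 1 PE x 21 weeks = 6 + 21 = 27 per subject, which reproduces the stated 27. SAP 3.3 plans 10 subjects: 10 x 27 = 270 sessions.

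**Step 4. Effect per session.** A session whose only reaction is related and does not recur adds 1/270 = 0.37 percentage points to the suspected-AR percentage and 0 to the AR percentage.

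**Step 5. Illustrations with assumed counts.** The documents give no reaction counts.

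- One such session per subject: suspected AR 10/270 = 3.7%, AR 0/270 = 0%.
- Two per subject: 20/270 = 7.4% against 0%.
- Three per subject: 30/270 = 11.1% against 0%.
- One subject's reaction ends PE at the first session, and no other reactions occur: the denominator is 9 x 27 + 1 = 244; suspected AR 1/244 = 0.41%, AR 0%.

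**Step 6. Illustration that allows recurrence.** Assume one reaction type with probability q per session, independent over 27 sessions, no one stopping, and every recurring reaction graded 'definite'. The documents do not say whether the first occurrence is upgraded once the reaction recurs, so both readings are shown:

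- first occurrence upgraded: AR% = q[1 − (1 − q)^26]
- only the second and later occurrences count: AR% = q − [1 − (1 − q)^27]/27

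| q = suspected-AR% (assumed) | AR%, first upgraded | AR%, second onward | Share of reaction sessions not counted |
|---|---|---|---|
| 1% | 0.23% | 0.12% | 77% to 88% |
| 2% | 0.82% | 0.44% | 59% to 78% |
| 5% | 3.68% | 2.22% | 26% to 56% |
| 10% | 9.35% | 6.51% | 6% to 35% |
| 20% | 19.94% | 16.31% | 0% to 18% |

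Under these assumptions the proportional shortfall is large for rare reactions and small for frequent ones.

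**The case against.** The strongest reply is that nothing is hidden. The strict tier is a disclosed protocol choice which the SAP follows faithfully. Related TEAEs are reported by subject and by event, discontinuations and SAEs have their own tables (14.3.2.2, 14.3.2.3), all AEs are listed (16.2.6.1), and Table 14.3.1.4 gives the all-cause session figure. With 10 planned subjects, only one derived percentage is absent. All of that stands, and it makes this a reporting gap rather than a contradiction. It does not supply the missing percentage: the subject and event tables do not convert into sessions, and the all-cause figure is only an upper limit.

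Second, grading in practice may depart from the written definition. Whether the cited algorithms allow 'definite' without rechallenge cannot be checked from the documents. That also stands, and it is why the point applies to the definition as written.

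Three stronger readings are tempting and should be resisted.

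- A reader might infer that every reaction that ends PE is excluded. Only one that ends PE before any re-exposure is.
- A reader might note that the 72-hour windows cover 78 to 81 of the 168 treatment days (46% to 48%: 15 to 18 days in the intensive phase plus 21 x 3 = 63 in maintenance, session time ignored) and infer that unrelated events inflate the all-cause percentage by that much. The figure is only the chance that a single AE at a random time within the 24 treatment weeks falls in a window. TEAEs are collected to Week 48, where the coverage is 78 to 81 of 336 days, or 23% to 24%.
- A reader might infer that procedure-related events are excluded from the AR count. The text is unclear rather than exclusive. SAP 6.3.8 defines AR in its study-drug paragraph and then says "Same rules will apply to define AEs related to study procedure", while Protocol 7.1.3.2 speaks of responses to a medicinal product or study treatment. The basis needs stating, but this is secondary.

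**Conclusion.** The point holds for the definition as written. The AR percentage per session excludes related reactions that never recur and those that end PE before any re-exposure, and the planned session tables only bracket the suspected-AR percentage. The size of any understatement is unknown. The 0.37 points per session in Step 4 assumes that all 270 planned sessions take place; the other comparisons rest on assumed counts or rates. The gap lies in the planned outputs and not in data collection, since causality grade and onset date and time are required AE fields in Protocol 7.1.3.7. It is an improvement worth making because it changes what can be said about tolerability per session, but it is not an error that invalidates the trial or conceals events.

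**What to change.** Keep the 'definite' AR percentage and make these changes:

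1. Footnote Table 14.3.1.3 to say that AR means 'definite' only.
2. Add to SAP 4.3, SAP 6.3.8 and Table 14.3.1.3 the percentage of PE sessions with at least one suspected AR in the same 72-hour window.
3. Classify each session once by its highest causality grade (definite, probable, possible, doubtful/unlikely). The existing rule, "worst case in terms of severity, causality, and seriousness will be chosen", applies per subject within SOC and PT and does not cover sessions.
4. State in SAP 6.3.8 whether both percentages use study-drug causality, study-procedure causality or both. Show procedure rows only if a procedure grade is recorded: Protocol 7.1.3.7 lists a single causality field, and Protocol 7.1.2 frames it as the relationship to the investigational product.

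The cost is a few table rows, a footnote and some sentences in the SAP, documented under SAP 6.1 because the plan is already marked final. No protocol variable is replaced. The downsides are a less favourable reported reaction rate and a doubtful/unlikely tier that may lie close to the all-cause figure, which is why the grades should be shown separately.
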